11.3 Sample Size and Power Calculation

11.3.1 Main Study

Trial simulation was carried out to evaluate the performance characteristics of the trial. For each scenario, 10,000 simulated trials were summarized to create the performance characteristics of that trial. Under the assumptions of equivalent effectiveness success rate at 55% and equivalent safety event rate at 8.6% in both groups, at an experiment-wise error rate of 0.05, an adaptive sample size of 250-500 (mean sample size of 417) will provide 80% power for trial success, meeting both effectiveness and safety endpoints, and 82.8% power and 87.4% power for meeting effectiveness and safety endpoints individually. The probability of early trial success is 36.8%. In the simulation, the non-inferiority margin is 15% for effectiveness and 8% for safety. The primary AE rate in the first 7-days is simulated as a Bernoulli random variable with a specified probability; the occurrence of effectiveness failure and timing of the failure are based upon a three-piece exponential time-to-failure model. The detailed descriptions of the simulation assumptions as well as simulation under various scenarios are summarized in Appendix A.

These trial simulations assume a primary AE rate of 8.6% for both Test and Control groups under the alternative hypothesis. Based on P030031/S011 data, the overall primary AE rate was 10.8%. However, this primary AE rate included 3 study subjects deemed primary safety failures solely due to hospitalization for AF recurrence. The incidence of primary AEs excluding those 3 subjects was 8.6%. Thus, an 8.6% primary AE rate is used for the purpose of trial simulations.

These trial simulations assume an equivalent success rate of 55% for both Test and Control groups under the alternative hypothesis using the chronic definition of effectiveness failures as defined in Section 8.1. These assumptions are based upon review of data from recent pivotal P030031/S011 AF THERMOCOOL® Trial where the chronic success rate in the NAVISTAR® THERMOCOOL® Group at 1 year follow-up was 62.7% (64/102) for all sites and 43.3% (29/67) for US data only. Therefore, it is estimated that the chronic success rate for both the nMARQ™ System and THERMOCOOL® at 12 month follow-up will be around 55%.

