11.5.1 Primary Safety Endpoint

The primary safety analysis is on the 7-day early onset event rate (except for PV stenosis and atrio-esophageal fistula). The AT population is used as the analysis population.

In order to have consistent mathematical notations for both effectiveness and safety endpoints, event-free rate is used for the safety hypothesis and analyses. The probability of a subject being event-free (success) in the experimental arm is α_2 and in the control arm is α_1 . The hypothesis of non-inferiority is

$$\alpha_2 > \alpha_1 - \delta_s,$$

where the non-inferiority δ_s value of 0.08 is used.

The posterior distribution for the failure-free rate is determined using a non-informative prior distribution (Beta(1,1) priors independently for each arm).

The claim of non-inferiority will be accepted if the posterior probability of non-inferiority is larger than 0.9675. That is, if,

$$\Pr(\alpha_2 > \alpha_1 - \delta_s | \text{ Trial Results}) \geq 0.9675$$

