11.5.2 Primary Effectiveness Endpoint

The primary effectiveness analysis is a non-inferiority test based on the 3 to 12 month failure-free rate. The ITT population is used as the analysis population based on the treatment group as randomized. Any missing data will be imputed using Bayesian multiple imputation as described in the 'Handling or Missing Data' section in this protocol.

The probability of a subject being failure-free (success) in the experimental arm is π_2 and in the control arm is π_1 . The hypothesis of non-inferiority is

$$\pi_2 > \pi_1 - \delta_E,$$

where the non-inferiority δ_E value of 0.15 is used.

The posterior distribution for the control failure-free rate calculated based on a non-informative prior distribution (Beta(1,1) priors independently for each arm).

The claim of non-inferiority will be accepted if the posterior probability of non-inferiority is larger than 0.980. That is, if,

$$\Pr(\pi_2 > \pi_1 - \delta_E | \text{Trial Results}) \geq 0.980$$

The critical values of 0.980 and 0.9675 for each of the two endpoints are used in order to control the experimentwise type I error for the trial given the adaptive design. The type I error of the design is controlled at the 0.05 one-sided level. The type I error control is demonstrated by the simulations in Appendix A.

The primary effectiveness analyses will also be performed in the AT and PP populations as sensitivity analyses.

If the primary effectiveness success rate is less than 40% for either the Test group or the Control group, then additional analyses will be conducted to examine the poor device performance as follows.

- 1) The subject demographic and baseline characteristics will be compared between the current study and the P030031/S011 study where the chronic effectiveness endpoint was 62.1% (64/103) with a 95% confidence interval of 50.7% to 72.7% using the exact binomial method; If there is major difference in some of the covariates predicting the primary effectiveness endpoint, then covariates adjusted analyses will be performed for the primary effectiveness endpoint in the current study.
- 2) Multivariate regression analyses will be performed to identify the characteristics predicting the low performance;
- 3) Subgroup analyses will be performed to examine the impact of the characteristics that drive the low performance (e.g. by site, operators, regions, age, gender, ablation parameters, LA size etc.)

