In each piece of the exponential function, the prior distribution is updated using the observed number of events and total exposure time from the data. The predictive distribution of each subject, and each prospective new subject, is calculated using this longitudinal modeling. From the gamma posterior distribution, 10,000 hazard rates were sampled. Based upon the 10,000 triplets of hazard rates for all of the three pieces, the probability of effectiveness success and event-free rate at 12 month follow-up time will be calculated. No baseline covariates were used in the imputation model.

As a sensitivity analysis at each interim analysis, including the early success analysis, the results for an 11-piece exponential model will be presented. This model is very flexible, and will provide robustness to the 3-piece model assumptions and the prior distributions used. The 11-piece exponential is:

The time-to-failure in treatment arm t is assumed piecewise exponential with eleven distinct intervals. The probability of a failure during each interval is exponentially distributed, with a different hazard rate per interval. The model is:

$$f(t) = \exp(-th(t)),$$

where

$$h(t) = \begin{cases} \gamma_{a,1} & 0 < t \leq 2 \\ \gamma_{a,2} & 2 < t \leq 4 \\ \gamma_{a,3} & 4 < t \leq 8 \\ \gamma_{a,4} & 8 < t \leq 12 \\ \gamma_{a,5} & 12 < t \leq 16 \\ \gamma_{a,6} & 16 < t \leq 20 \\ \gamma_{a,7} & 20 < t \leq 24 \\ \gamma_{a,8} & 24 < t \leq 28 \\ \gamma_{a,9} & 28 < t \leq 32 \\ \gamma_{a,10} & 32 < t \leq 36 \\ \gamma_{a,11} & 36 < t \leq 39 \end{cases} .$$

The exponential parameter in each interval is a function of the interval and the treatment arm (a=1 is control; a=2 is experimental). The prior distribution for each exponential parameter is assumed to be very weak. The independent priors are (in the scale of weeks)

$$[\gamma_{a,j}] \sim \text{Gamma}(0.001, 0.001) \quad \text{for } a=1,2; j=1,\dots,11.$$

For the safety outcome there is no interim information available on subjects and so there is no longitudinal aspect for safety. In order to multiply impute final data for the adverse event rate we simulate the probability of a successful (no primary adverse event) using independent Beta(1,1) distributions.

Additional frequentist sensitivity analyses will be used to test the robustness of the primary effectiveness results with regards to missing data. They include but not limited to the following:

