11.6.2 Sample Size Interim Analyses

Interim looks are made before accrual is stopped. At these looks predictive probabilities of trial success (both efficacy and safety) for the current sample size and the maximum sample size are calculated. All interim results available are used to calculate the predictive probability of trial success for the currently accrued subjects. A longitudinal model (as described in Section 11.5.4) is used for the prediction of subjects with incomplete efficacy data. A decision is made whether to stop at the current sample size or to continue accrual. These sample size looks are made at sample sizes of 250 enrolled, and then every 50 subjects enrolled until accrual stops or the maximum sample size of 500 is reached. Let PP_n be the predictive probability of trial success for a trial with the current sample size of n and PP_{max} the predictive probability of trial success if the trial is carried out to the maximum sample size (500). The following rules are used to guide the sample size selection. These predictive probabilities are probabilities of winning on both the efficacy and safety endpoints.

If $PP_n > S_n$ then the sample size is considered sufficient for non-inferiority, and accrual stops. If $PP_{max} < 0.05$ then accrual is stopped for futility. The cut-offs for expected success are:

n	S_n
250, 300	0.95
300, 350, 400, 450	0.90

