11.6.3 Early Success Claim Interim Analyses

An interim analysis will be conducted 16 weeks after enrollment ends for early success. If the predictive probability of final success is greater than 99%, then trial success will be declared early. All subjects will have complete safety data and all subjects will be followed through their trial completion.

Trial simulations are carried out in order to evaluate the performance (operating) characteristics of the trial. The simulations mimic the design exactly as described above. The same models are simulated as will be used in the design. The timing of the trial is also mimicked. The efficacy period is after a 12-week blanking period, and lasts 39 weeks. The safety endpoint is assumed known for all subjects in the trial (in practice there will be a handful that do not have complete safety data). Simulation details are attached in Appendix A.

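### The unconditional 0.05 type I error statement does not hold over the whole safety null: the limit is about 0.078 if safety is complete at every look, and about 0.05-0.06 with a handful of subjects pending

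*Protocol*

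**What the plan says.** Trial success requires both co-primary endpoints (Protocol 11.5). For safety, "The claim of non-inferiority will be accepted if the posterior probability of non-inferiority is larger than 0.9675" (11.5.1), with Beta(1,1) priors and a margin of 0.08. Effectiveness uses a cut-off of 0.980 and a margin of 0.15 (11.5.2). The same section says the two cut-offs were chosen to control the experiment-wise error under the adaptive design, and continues: "The type I error of the design is controlled at the 0.05 one-sided level". As support it adds: "The type I error control is demonstrated by the simulations in Appendix A". Section 11.3.1 also says the assumptions and "simulation under various scenarios are summarized in Appendix A".

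Sample size looks are made at 250, 300, 350, 400 and 450, with a cap of 500. If the predictive probability of success on both endpoints exceeds the cut-off S_n, "then the sample size is considered sufficient for non-inferiority, and accrual stops" (11.6.2). Accrual stops for futility if predicted success at 500 is below 0.05.

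On safety data at a look, 11.5.4 says "For the safety outcome there is no interim information available on subjects and so there is no longitudinal aspect for safety". Section 11.6.3 says of the simulations: "The safety endpoint is assumed known for all subjects in the trial". It adds that in practice a few subjects will have incomplete safety data.

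SAP section 10.0 recounts the experiment-wise rate of 0.05 from the protocol.

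**The concern.** The null for a two-endpoint claim is every case in which either endpoint fails its margin. It includes a device that is more effective than control and 8 points worse on primary adverse events. There the safety test has to protect on its own. If safety is complete at a look and effectiveness is close to certain, predicted success depends only on whether safety passes on the current data. Accrual then stops at the first size where it does. That gives up to six chances at an unchanged cut-off, each with error slightly above the nominal 1 - 0.9675 = 0.0325. At stake is whether the 0.05 statement is true as written for the co-primary that guards against harm.

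**Working it through.** **Inputs.** Cut-offs, margins, priors, looks and futility rule are as above. S_n is 0.95 at 250 and 300, and 0.90 at 350-450. The planning rates of 55% effectiveness and 8.6% adverse events come from Protocol 11.3.1. The safety null is 8.6% control against 8.6 + 8.0 = 16.6% test. Allocation is 1:1, so the sizes are 125, 150, 175, 200, 225 and 250 per arm. The accrual rate is not in the supplied text and is an assumption wherever it enters.

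**Step 1: the plan's own figures.** The full design was simulated twice with separately written code, using the three-piece exponential model and its stated priors. At equal rates of 55% and 8.6%:

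| | Joint power | Effectiveness | Safety | Mean N |
|---|---|---|---|---|
| Protocol 11.3.1 | 80% | 82.8% | 87.4% | 417 |
| Simulation A, 8 per week | 79.9% | 82.8% | 86.8% | 413 |
| Simulation B, 9 per week | 79.5% | 82.4% | 86.5% | 420 |

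Power and mean N reproduce closely. The stated early-success probability of 36.8% does not: A gives 47-51% and B gives 44.6%. Counting only trials that stop before 500, A gives 35-37%, but the text does not say which count is meant.

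**Step 2: error at one size, exact.** With s event-free subjects out of n in an arm, the posterior is Beta(1 + s, 1 + n - s). Safety passes if Pr(α₂ > α₁ - 0.08 | data) ≥ 0.9675. Summing binomial probabilities over the passing region at 91.4% and 83.4% event-free gives 0.0338-0.0348 across the six sizes.

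**Step 3: error over six sizes, exact.** Start from the joint distribution at 125 per arm, remove the paths that pass, add 25 per arm, and repeat.

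| Total N | 250 | 300 | 350 | 400 | 450 | 500 |
|---|---|---|---|---|---|---|
| Newly passing | 0.0344 | 0.0127 | 0.0098 | 0.0075 | 0.0069 | 0.0062 |
| Cumulative | 0.0344 | 0.0471 | 0.0569 | 0.0644 | 0.0713 | 0.0775 |

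With control rates of 5% and 13% the last figure is 0.0784 and 0.0755. A declared success needs safety to pass on complete data at the stopping size. So this is an upper limit for any accrual rate, reporting lag or effectiveness model.

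**Step 4: full design, safety complete at each look.** Simulation A, safety null, control effectiveness 55%, futility rule applied, 10,000 trials per cell (standard error 0.002-0.003), by assumed accrual per week:

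| Test effectiveness | 2 | 3 | 5 | 8 | 14 |
|---|---|---|---|---|---|
| 55% | 0.053 | 0.050 | 0.049 | 0.041 | 0.035 |
| 65% | 0.074 | 0.068 | 0.070 | 0.063 | 0.047 |
| 75% | 0.076 | 0.075 | 0.075 | 0.072 | 0.056 |

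Simulation B agrees. At equal effectiveness it gives 0.056, 0.051, 0.044, 0.038, 0.033 and 0.033 at 1.5, 3, 7, 10, 15 and 25 per week. With test effectiveness of 65% it gives 0.071 and 0.060 at 3 and 10 per week; with 80%, 0.079 and 0.069. The 0.079 is within simulation error of the exact limit (standard error 0.0025). On the effectiveness null (55% against 40%) the error is only about 0.018-0.021.

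**Step 5: some safety data pending.** Effectiveness is taken as certain, with the futility rule applied. Two sets of runs:

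| Pending at each look | 0 | 2 | 8 | 12 | 16 | 32 | 52 |
|---|---|---|---|---|---|---|---|
| First set | 0.076 | 0.056 | 0.059 | 0.051 | 0.052 | 0.043 | 0.039 |
| Second set | 0.074 | 0.061 | 0.056 | - | 0.052 | 0.043 | - |

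A borderline pass with outcomes still to come often falls short of S_n, so accrual continues past it. Simulation A with a one-week safety lag is consistent. At 75% test effectiveness it gives 0.057 at 2 per week (about 2 × 1 = 2 pending) and 0.054 at 8 per week (about 8 pending).

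**The case against.** The strongest reply is that 0.078 describes a trial nobody would run: it needs no pending safety data at any look, and section 11.6.3 itself expects a few incomplete subjects. Two pending subjects remove most of the excess. Late pulmonary vein stenosis and atrio-esophageal fistula also count after day 7, so real safety data may be less complete still. This stands. A reader might infer that the trial as conducted carried an error of 0.078, and the documents do not support that. The figure is a ceiling under the protocol's own simulation assumption.

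Second, the case requires a device that is both more effective and 8 points less safe, whereas the protocol plans on equality. At equal effectiveness the error is about 0.04 at the accrual that fits the stated mean N (0.041 at 8 per week). This is true, but the sentence in 11.5.2 is not limited to equal effectiveness.

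Third, Appendix A is cited as the demonstration and was not among the supplied documents. A reader might infer that the sponsor left these nulls out or set no limits on the claim. That cannot be concluded, because the appendix may list them. It would not rescue the unconditional wording, since step 3 follows from the stated rules alone.

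Fourth, accrual is assumed and the early-success figure is not matched. That weakens step 4, but the limit in step 3 uses neither. The only timing in the text is a 4.5-year enrollment phase that includes a suspension (Protocol 6.5). For 500 subjects that averages 500 / 234.8 weeks = 2.1 per week, so the active rate was higher.

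**Conclusion.** The point holds in a limited form. As written, the 0.05 one-sided statement is not true over the whole safety null. With safety complete at every look the exact limit is about 0.078. With a handful pending the error is about 0.05-0.06 even if effectiveness is certain, and it is below 0.05 at about 30 pending. At equal effectiveness it runs from about 0.03 to 0.056 with assumed accrual, and is at or below 0.05 at the 8-9 per week that fits mean N. The excess is confined to the safety null. The limit rests only on the stated rules; the other figures rest on assumed accrual or pending counts and on simulations not shown to be the sponsor's own.

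Two further inferences are not supported. The S_n table lists n = 300 under 0.95 and again in the row "300, 350, 400, 450" at 0.90, but this does not drive the result: the error is 0.0608 with one value and 0.0605 with the other. Nor is any closeout conclusion affected. The 250-subject look was run (SAP 12.5), but the SAP supersedes the protocol methods (2.0), cancels the 300-subject look (3.2), makes no inference (8.0) and reports no efficacy (12.0). This is a minor correction to an error statement.

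**What to change.** Qualify the sentence in Protocol 11.5.2, and note the same limit where SAP 10.0 recounts the rate. For example: *Type I error is at most 0.05 in the scenarios simulated in Appendix A. On the safety null with a more effective test arm it can exceed 0.05, with an upper limit of about 0.08 if safety is complete at every look and about 0.05-0.06 if a handful of subjects are pending.*

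Before adopting these values, run safety-null cases with test effectiveness above control in the sponsor's own simulation code, with and without pending safety data. As a separate clerical correction, give n = 300 a single S_n value in 11.6.2.

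The cost is one sentence, one cross-reference, one table row and a few extra runs of existing code. The stated error rate becomes less favourable. No change of cut-off is proposed.

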11.5.3 Site Heterogeneity

Each site should not enroll more than 20% of the total enrollment to minimize the possibility that the study results could be highly influenced by a few sites. We will combine sites with less than five randomized subjects according to the geographic regions. Using this pre-determined criterion, sites with less than five randomized subjects within the same geographic region will be

combined such that the combined center(s) would have five or more randomized subjects and no more than 5 sites combined.

Although the primary endpoint analyses are based on a Bayesian framework, site heterogeneity will be investigated using a set of frequentist analyses. A Breslow-Day test will be conducted to examine the homogeneity across sites for the associations of the primary effectiveness and safety endpoints with treatment groups. A p-value less than 0.15 will be considered statistically significant for an assessment of homogeneity across the treatment sites. A non-significant result, or a significant result that is only quantitative in nature, will support pooling of sites for the primary analyses. If the sites are not poolable, the following additional sensitivity analyses will be performed:

1. GEE models with the primary endpoints as the outcome and a fixed effect for treatment and a random effect for site will be used to estimate the treatment effect adjusting for site.
2. Logistic regression models with the primary endpoints as the outcome and fixed effects for treatment and site will be used to estimate the treatment effect adjusting for site.

If the sites are determined not to be poolable, then the overall treatment effect and its confidence interval will be estimated from the model in which sites are treated as random effects for the primary safety and effectiveness analysis. The claim of trial success will be based upon the totality of the data. The sensitivity analyses treating sites as random effects examine the impact of site heterogeneity on the primary endpoints.

11.5.4 Handling of Missing Data

The primary effectiveness analysis will use the ITT population and as such there is potential for subjects to have missing data. Any missing data in this analysis will be imputed using Bayesian multiple imputation method. This approach will enable the primary effectiveness analysis to be done on the full ITT population. The subjects who discontinued the study due to device related reasons will be treated as primary effectiveness failures in the ITT population.

In the adaptive design interim analyses and at the trial completion, the following longitudinal model is used to handle incomplete and missing data. The posterior distribution of the effectiveness success rate is updated using multiply imputed data from each subject with incomplete data⁷¹. The model is a piecewise exponential model, with different parameters for each treatment arm. The following model is used for the time-to-failure during the effectiveness observation phase (13-52 weeks after procedure).

The time-to-failure in treatment arm t is assumed piecewise exponential with three distinct intervals (from (0,2], (2,8], and (8,39] weeks). The probability of a failure during each interval is exponentially distributed, with a different hazard rate. The model is:

$$f(t) = \exp(-th(t)),$$

where

$$h(t) = \begin{cases} \gamma_{a,1} & 0 < t \leq 2 \\ \gamma_{a,2} & 2 < t \leq 8 \\ \gamma_{a,3} & 8 < t \leq 39 \end{cases} .$$

The exponential parameter in each interval is a function of the interval and the treatment arm (a=1 is control; a=2 is experimental). The prior distribution for each exponential parameter is based on the data from the THERMOCOOL[®] Pivotal trial, on the THERMOCOOL[®] arm. The following priors, down weighted by a factor of 5 (meaning the data from each subject in the historical study is weighed as 1/5 of a subject). This downweighting is used to insure the prospective trial data for each arm is weighed more heavily. The independent priors are (in the scale of weeks)

$$[\gamma_{a,1}] \sim \text{Gamma}(26/5, 160.8/5)$$

$$[\gamma_{a,2}] \sim \text{Gamma}(3/5, 416.8/5),$$

and

$$[\gamma_{a,3}] \sim \text{Gamma}(7/5, 1652.4/5).$$

In each piece of the exponential function, the prior distribution is updated using the observed number of events and total exposure time from the data. The predictive distribution of each subject, and each prospective new subject, is calculated using this longitudinal modeling. From the gamma posterior distribution, 10,000 hazard rates were sampled. Based upon the 10,000 triplets of hazard rates for all of the three pieces, the probability of effectiveness success and event-free rate at 12 month follow-up time will be calculated. No baseline covariates were used in the imputation model.

As a sensitivity analysis at each interim analysis, including the early success analysis, the results for an 11-piece exponential model will be presented. This model is very flexible, and will provide robustness to the 3-piece model assumptions and the prior distributions used. The 11-piece exponential is:

The time-to-failure in treatment arm t is assumed piecewise exponential with eleven distinct intervals. The probability of a failure during each interval is exponentially distributed, with a different hazard rate per interval. The model is:

$$f(t) = \exp(-th(t)),$$

where

$$h(t) = \begin{cases} \gamma_{a,1} & 0 < t \leq 2 \\ \gamma_{a,2} & 2 < t \leq 4 \\ \gamma_{a,3} & 4 < t \leq 8 \\ \gamma_{a,4} & 8 < t \leq 12 \\ \gamma_{a,5} & 12 < t \leq 16 \\ \gamma_{a,6} & 16 < t \leq 20 \\ \gamma_{a,7} & 20 < t \leq 24 \\ \gamma_{a,8} & 24 < t \leq 28 \\ \gamma_{a,9} & 28 < t \leq 32 \\ \gamma_{a,10} & 32 < t \leq 36 \\ \gamma_{a,11} & 36 < t \leq 39 \end{cases} .$$

The exponential parameter in each interval is a function of the interval and the treatment arm (a=1 is control; a=2 is experimental). The prior distribution for each exponential parameter is assumed to be very weak. The independent priors are (in the scale of weeks)

$$[\gamma_{a,j}] \sim \text{Gamma}(0.001, 0.001) \quad \text{for } a=1,2; j=1,\dots,11.$$

For the safety outcome there is no interim information available on subjects and so there is no longitudinal aspect for safety. In order to multiply impute final data for the adverse event rate we simulate the probability of a successful (no primary adverse event) using independent Beta(1,1) distributions.

Additional frequentist sensitivity analyses will be used to test the robustness of the primary effectiveness results with regards to missing data. They include but not limited to the following:

1. Kaplan-Meier analysis: this analysis will include all subjects in the ITT population and missing data will be censored at their last observations. The analyses will be stratified by the two treatment groups as randomized. Non-inferiority testing will be performed using the survival probabilities of the two treatment groups at 12 months follow-up.
2. The success rate at 6, 9 and 12-month will be presented for subjects in the ITT population treating the endpoint as a binary variable. The subjects who discontinued the study due to device related reasons will be treated as primary effectiveness failures in the ITT population. Other subjects with missing effectiveness outcomes will be excluded from the analyses. The point estimate for each treatment arm and the one-sided 95% confidence interval around the point estimate will be presented. The point estimate around the treatment difference (nMARQ-TC) and the one-sided 95% confidence interval around the difference will also be presented.

3. Tipping-point analysis: to examine the sensitivity of conclusions to missing data.

Tipping-point analysis will also be used as sensitivity analysis for the primary safety endpoint.

